1. INTRODUCTION AND RATIONALE

Sciatica is a condition of radicular pain in the leg and is usually caused by herniation of a lumbar intervertebral disc. The herniated disc compresses a lumbar nerve root that continues its route into the sciatic nerve. About 13% to 40% of all people will suffer from sciatica at least once during their lifetime [1]. Sciatica can have severe socio-economic effects; patients are immobilised by the pain they experience and therefore cannot go to work or participate in social events.

Most cases resolve spontaneously with conservative therapy using only standard analgesics and/or physiotherapy. In a large RCT it was demonstrated that outcome of conservative and surgical therapy was comparable after 26 weeks [2]. 40% of patients randomized to the conservative care group crossed over and was treated surgically, with a mean delay of 15 weeks. With this knowledge the guidelines for surgical treatment of sciatica were adjusted and it is nowadays usual care to offer surgery only after at least 8 weeks of conservative care and preferably after 14-16 weeks of conservative care. This decision is made together with the patient in a process of Shared Decision making [3,4].

Although this treatment regimen has been demonstrated to be efficacious and cost effective, the burden for a patient during these weeks of conservative care is usually high. We seek to find a type of conservative care to reduce the discomfort due to the pain and to enable the patient to remain physically active. Not only will this add to the quality of life of the patient, but it will also prevent the patient from taking a sick-leave.

Rationale for this study

We would like to explore the effectivity of the transforaminal epidural injection (TEI) with analgesic and anti-inflammatory medication to relieve the symptoms. Theoretically, such an injection would have a painkilling effect within the first two weeks after injection, and this effect may last for months, but we know that some patients do not experience this beneficial effect [5]. Some patients report initial pain reduction but report a re-arousal of pain after several hours, days or weeks [6].

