2. OBJECTIVES

Primary study objective:

To study effectivity of the epidural injection with analgesic and anti-inflammatory medication to relieve the symptoms within two weeks follow up.

It will be evaluated what the average leg pain score is in both treatment arms at two weeks follow up. It will be evaluated how long the effect lasts.

The leg pain and functionality at 4 weeks after randomization will also be evaluated to get informed on the responsiveness on TEI in a somewhat later stage.

Secondary study objectives:

To evaluate the outcome of TEI in the first two weeks after randomization as a predictor of NRS leg pain at 14-16 and ca 26 weeks after onset of leg pain.

Ideally, responsiveness to TEI can predict the clinical condition at 14-16 weeks after onset of sciatica. The hypothesis is that being non-responsive to TEI within two weeks, predicts an unsatisfactory condition after 14-16 weeks of suffering. This is the category of patients that in contemporary care in the Netherlands will be offered a surgical intervention. If our hypothesis is correct, in the future, this population of patients can be offered a surgical intervention at an earlier time point.

The ca 26-week time point is chosen since in the Sciatica trial [2], both the conservative and the surgical group demonstrated comparable outcome data.

Patients in this study are included while suffering from severe leg pain for 3-8 weeks.

Presumably most patients will enter the study with 4-6 weeks of leg pain. This means that on average 10 weeks after randomization, the 14-16 week leg pain time point is reached. This means that 21 weeks after randomization the ca 26-week leg pain time point is reached.

The response in NRS leg pain, ODI and patient satisfaction at 1 week after injection and at 2 weeks after injection will be correlated to the value of these parameters at 10 and 21 weeks after randomisation.

To evaluate the cost-effectivity of analgesic/anti-inflammatory epidural injections to relieve symptoms of early sciatica.

A substantial portion of the patients in this study will eventually have an MRI of the lumbar spine. These MRIs will be evaluated according to our standard MRI evaluation protocol, that has been proven to generate additional successful conclusions and subsequent publications in the past [10-15]. Protruding disc, disc and vertebral end plate changes (MODIC) will be correlated to clinical data.

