3. STUDY DESIGN

This is a prospective, open-label, randomized controlled trial on patients suffering from acute sciatica (3-8 weeks pain in the leg with a NRS ≥ 6) (see inclusion and exclusion criteria) in which consecutive patients who meet the inclusion criteria are invited to participate in the trial. The trial will take place at the Spaarne Gasthuis Hospital (SG) in Hoofddorp and Haarlem, the Netherlands in cooperation with researchers from Leiden University Medical Center (LUMC), Leiden, the Netherlands. Patient recruitment will occur at GP practices (GP collective Haarlemmermeer and Kennemerland, 185 GP's). The GP will diagnose the patient and, if the patient is diagnosed with sciatica, refer to the study investigator.

Eligible patients that are willing to participate are randomized to treatment with transforaminal epidural injections (treatment group) or standard conservative care (control group).

Randomization will take place using block randomization in a 1:1 allocation ratio. Patients from the treatment group will be treated with TEI, oral pain medication and, if deemed necessary by the GP, physiotherapy. The control group will only receive oral pain medication and if deemed necessary additional physiotherapy. For this study, the control group will not include placebo injections since we want to compare treatment with injections to treatment without injections. The focus will not be on the type of medication that is contained in the injection. Furthermore, a control group without injections will demonstrate what percentage of patients will experience spontaneous relief of symptoms (only using medication and/or physiotherapy) as it is known that in a significant part of the patients sciatica resolves without any intervention.

At baseline, clinical and demographic data are gathered for patients in both groups. Patients from the treatment group will receive TEI within 4 days after randomization. Patients from this group can receive multiple injections but an injection is only repeated after a certain interval time according to usual anaesthesiological guidelines. For all injections, details on timing, frequency and prevailing complications will be gathered.

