NRS leg pain that decreases below the value of 4 (on a 10 point scale) within two weeks after TEI is documented as successful effect of TEI. NRS leg pain that remains higher than a value of 4 at a time interval of two weeks after TEI makes a patient eligible for surgery if the patient requests for surgery. If surgery is requested by the patient (either in the control or intervention group), general guidelines for timing of surgery will be conducted, meaning that the patient is encouraged to postpone surgery till 14-16 weeks after onset of pain. This decision is made using Shared Decision Making and it is possible that the patient is operated before the 14-16 week time point. The patients who are randomized cannot be operated in the first two weeks after randomization, unless sudden loss of strength or a cauda equina syndrome is reported. We expect that during these two weeks TEI will have its effect. Four

weeks after randomization the outcome parameters are measured again to be informed on the late effect of TEI. Patients will be followed up for a total duration of 21 weeks starting from the moment of randomization. Questionnaires will be filled in at baseline, 1, 2, 4, 10 and 21 weeks follow-up. A schematic overview of the study procedures is outlined in figure 1. Note that this figure does not hold into account that it is possible for patients randomized to the treatment group to receive additional injections if necessary.

[figure not shown]

Fig.1 Flow diagram of study procedures

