8.2 Secondary study parameter(s)

The absolute decline in NRS leg pain, NRS back pain and ODI and increase in EQ5D from baseline to 2 weeks after randomization will be calculated using t-tests. The same will be done for the baseline to 4 weeks after randomization time point (using t-tests).

Perceived recovery Likert data will be dichotomized (1 and 2 is success, 3-7 is no success) and compared at 2 and 4 weeks after randomization or injection and to 14 and 26 weeks after start of severe leg pain using Chi-square tests.

The 2-week success data will be correlated to the success data after 14 weeks and subsequently for 26 weeks using Chi-square tests to make predictions. Logistic regression analysis will be used to correlate 2-week (and 4-week) success data to the absolute data for NRS leg pain, NRS back pain, ODI, increase in EQ5D at 14 and 26 weeks.

Cost effectiveness analysis:

The economic evaluation will consist of a cost-effectiveness analysis from a healthcare perspective (CEA: costs per extra patient with symptom relieve, i.e. the primary outcome measure) and a cost-utility analysis from a societal perspective (CUA: costs per QALY). Both analyses will be trial-based, using patient reports, with a half-year time horizon. Healthcare use will be valued according to the Dutch guidelines. QALYs will be calculated as the area under the utility curve, estimated using the Dutch tariff for the EQ-5D. As sensitivity analysis, QALYs will also be calculated using the VAS for quality of life (with power transformation). Average costs and patient outcome will be compared according to intention-to-treat, using net-benefit analysis, and using multiple imputation to account for missing data.

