10.6 Public disclosure and publication policy

The results from this trial will be published in international peer reviewed journals. Results will be presented on international spine and pain congresses. Furthermore, the results can influence the usual care in the Netherlands and will subsequently be offered to be considered by (inter)national guideline-authors for treatment of sciatica.

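### Section 2 moves from predicting a poor later condition to an earlier surgical offer, but the plan can show only prognosis and does not commit to reporting how accurate the predictor is

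*Combined protocol and SAP*

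**What the plan says.** Section 2 (Objectives) sets out a secondary, prognostic aim: "The hypothesis is that being non-responsive to TEI within two weeks, predicts an unsatisfactory condition after 14-16 weeks of suffering". It then notes that patients in that condition are the ones to whom Dutch practice currently offers surgery, and concludes: "If our hypothesis is correct, in the future, this population of patients can be offered a surgical intervention at an earlier time point".

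Section 3 (Study design) randomises TEI against standard conservative care, 1:1. Timing of surgery is not part of the randomisation. In both arms a patient who asks for surgery is handled under general guidelines, "meaning that the patient is encouraged to postpone surgery till 14-16 weeks after onset of pain", and shared decision making may lead to an earlier operation. Apart from two emergency exceptions, surgery is ruled out only in the first two weeks after randomisation. Repeat injections are allowed in the TEI arm.

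Section 8.2 (Secondary study parameters) gives the analysis: "The 2-week success data will be correlated to the success data after 14 weeks", and then to 26 weeks, by chi-square test as the basis for prediction. Logistic regression relates 2- and 4-week success to later pain, disability and EQ-5D values. Predictive values are not mentioned, nor is surgery that takes place before the later measurements.

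Section 10.6 expects that "the results can influence the usual care in the Netherlands" and that results will be put to guideline authors.

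**The concern.** The sentence in section 2 makes an earlier surgical offer depend on one condition, that the prognostic hypothesis is correct. Two further steps lie between that hypothesis and the offer.

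- **Accuracy.** Bringing forward an offer that would come later anyway makes sense only if the predictor picks out, patient by patient, those who will reach that point. A significant association in a group does not establish this.
- **Effect of timing.** Whether non-responders fare better with earlier than with later surgery is a causal question about a treatment that the trial neither assigns nor compares.

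At stake is how a positive secondary result would be read. A small p-value could be taken as the hypothesis being correct, and so as support for a change in practice, without anyone having reported how often the prediction is wrong.

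**Working it through.** **The plan's own figure.** Section 4.4 uses a difference of 1.5 points, SD 2.6, 90% power and a 5% level (taken as two-sided). n per group = 2 × (1.960 + 1.282)² × 2.6² / 1.5² = 63.1, so 64, as stated. Allowing for 10% loss, 128 / 0.9 = 142.2 (142 stated), or 71 randomised per arm. This calculation is for the primary endpoint and is not in dispute. No sample size or precision is given for the prediction aim.

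**Number of non-responders.** Section 1 quotes an average of 33%.
- 0.33 × 64 = 21.1
- 0.33 × 71 = 23.4

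That is about 21-23 patients. The 33% comes from a cited study in which response was seen within hours of the injection. Section 3 instead defines success as NRS leg pain below 4 within two weeks. With the planning mean of 4.0 for the TEI arm and a roughly normal distribution, about half would be at or above 4: 0.5 × 64 = 32 to 0.5 × 71 = 35.5.

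**Can the planned test be significant with a weak predictor?** Illustrative counts (assumed, not from the documents), 64 TEI patients:

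| | Poor later | Satisfactory later | Total |
|---|---|---|---|
| Non-responders | 10 | 11 | 21 |
| Responders | 9 | 34 | 43 |
| Total | 19 | 45 | 64 |

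- Uncorrected chi-square = 64 × (10×34 − 11×9)² / (21 × 43 × 19 × 45) = 64 × 241² / 772,065 = 4.81, p = 0.028.
- With continuity correction = 64 × (241 − 32)² / 772,065 = 3.62, p = 0.057.
- Predictive value of non-response for a poor condition = 10/21 = 48%, so 11/21 = 52% of non-responders have a satisfactory later condition.

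Section 8.2 does not say which form of the test is used. With the uncorrected form, this table is significant at 5% while the prediction is wrong for about half of those flagged.

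**How precisely could a predictive value be estimated?** Wilson 95% interval: [p + z²/2n ± z√(p(1−p)/n + z²/4n²)] / (1 + z²/n), with z² = 3.84.
- Assumed 15/21 = 71%: centre (0.714 + 0.091)/1.183 = 0.681, half-width 1.96 × √(0.00972 + 0.00218)/1.183 = 0.181. Interval 50% to 86%.
- If half are non-responders, assumed 23/32 = 72%: centre (0.719 + 0.060)/1.120 = 0.695, half-width 1.96 × √(0.00632 + 0.00094)/1.120 = 0.149. Interval 55% to 84%.

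**Is timing of surgery compared anywhere?** Section 3 randomises the injection only and leaves timing to guidelines and shared decision. The tests and models in 8.2 contain no term for surgery. No other section plans a comparison of earlier with later surgery.

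**The case against.** The strongest reply is that the protocol does not claim that earlier surgery gives better results. The sentence just before the quoted one says that such patients are offered surgery in current care. On that reading an early predictor only identifies sooner those who would get the offer later. The wording is conditional and about the future, the aim is secondary, and section 3 already allows surgery before 14-16 weeks by shared decision. All of this stands, and it makes the point smaller. It does not remove it: bringing forward an offer still rests on accuracy in individual patients, which the plan does not commit to reporting.

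A reader might also infer some stronger points that the documents do not support:

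- **That a significant chi-square is the protocol's rule for changing surgical timing.** No section says so. Logistic regression is planned as well, and the 2×2 table behind the chi-square already contains the predictive values; the plan simply does not say that they will be reported.
- **That the protocol's background contradicts earlier surgery.** Section 1 reports that "outcome of conservative and surgical therapy was comparable after 26 weeks". That trial is not described as selecting TEI non-responders, 40% of its conservative arm crossed over to surgery, and the finding concerns the later state. The protocol's stated worry is the burden during the waiting weeks. The citation leaves the question open.
- **That non-responders with a good later score would have recovered without surgery.** An operation or a repeat injection can come before week 10 or 21, so one minus the predictive value does not measure spontaneous recovery.
- **That the trial is underpowered for earlier versus later surgery.** No such comparison is planned, so its power is not a defect of the plan.
- **That section 10.6 announces advice on surgical timing.** It speaks of the results in general.

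**Conclusion.** The concern holds in a limited form. A positive result would show that 2-week non-response carries prognostic information. It would not show that the prediction is accurate enough for individual patients unless predictive values are reported, and it could not show a benefit from changed timing. Because surgery before the 10- and 21-week measurements is not accounted for in 8.2, even the prognostic association may be blurred: a good later score in a non-responder may follow an operation.

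On size, about 21-23 non-responders at the quoted 33%, or about 32-36 if NRS below 4 is the criterion, would carry the estimate. An assumed predictive value near 71% would have an interval of roughly 50% to 86% at the smaller number. The 10/21 versus 9/43 split and the 71% are illustrations; the documents give no predictive value. The 32-36 also assumes an approximately normal score.

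Randomisation, sample size, primary analysis and conduct are untouched. This is a worthwhile correction to a secondary claim, not a flaw in the main comparison.

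**What to change.** 1. In section 2, state that a positive result shows prognostic value only, and that any change in the timing of surgery would need a separate comparison.
2. In section 8.2, alongside the chi-square, report the positive and negative predictive values of 2-week response and non-response in the TEI arm for the later outcome, with 95% confidence intervals, naming the success definition used.
3. In the same table, show how many responders and non-responders had surgery before the 10-week and before the 21-week measurement.

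Section 10.1 already provides for collecting data on lumbar surgery from the hospital record, so no new data stream should be needed. The cost is a more modest claim in section 2 and one added table. No surgical rule or timing is proposed here.

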3. STUDY DESIGN

This is a prospective, open-label, randomized controlled trial on patients suffering from acute sciatica (3-8 weeks pain in the leg with a NRS ≥ 6) (see inclusion and exclusion criteria) in which consecutive patients who meet the inclusion criteria are invited to participate in the trial. The trial will take place at the Spaarne Gasthuis Hospital (SG) in Hoofddorp and Haarlem, the Netherlands in cooperation with researchers from Leiden University Medical Center (LUMC), Leiden, the Netherlands. Patient recruitment will occur at GP practices (GP collective Haarlemmermeer and Kennemerland, 185 GP's). The GP will diagnose the patient and, if the patient is diagnosed with sciatica, refer to the study investigator.

Eligible patients that are willing to participate are randomized to treatment with transforaminal epidural injections (treatment group) or standard conservative care (control group).

Randomization will take place using block randomization in a 1:1 allocation ratio. Patients from the treatment group will be treated with TEI, oral pain medication and, if deemed necessary by the GP, physiotherapy. The control group will only receive oral pain medication and if deemed necessary additional physiotherapy. For this study, the control group will not include placebo injections since we want to compare treatment with injections to treatment without injections. The focus will not be on the type of medication that is contained in the injection. Furthermore, a control group without injections will demonstrate what percentage of patients will experience spontaneous relief of symptoms (only using medication and/or physiotherapy) as it is known that in a significant part of the patients sciatica resolves without any intervention.

At baseline, clinical and demographic data are gathered for patients in both groups. Patients from the treatment group will receive TEI within 4 days after randomization. Patients from this group can receive multiple injections but an injection is only repeated after a certain interval time according to usual anaesthesiological guidelines. For all injections, details on timing, frequency and prevailing complications will be gathered.

NRS leg pain that decreases below the value of 4 (on a 10 point scale) within two weeks after TEI is documented as successful effect of TEI. NRS leg pain that remains higher than a value of 4 at a time interval of two weeks after TEI makes a patient eligible for surgery if the patient requests for surgery. If surgery is requested by the patient (either in the control or intervention group), general guidelines for timing of surgery will be conducted, meaning that the patient is encouraged to postpone surgery till 14-16 weeks after onset of pain. This decision is made using Shared Decision Making and it is possible that the patient is operated before the 14-16 week time point. The patients who are randomized cannot be operated in the first two weeks after randomization, unless sudden loss of strength or a cauda equina syndrome is reported. We expect that during these two weeks TEI will have its effect. Four

weeks after randomization the outcome parameters are measured again to be informed on the late effect of TEI. Patients will be followed up for a total duration of 21 weeks starting from the moment of randomization. Questionnaires will be filled in at baseline, 1, 2, 4, 10 and 21 weeks follow-up. A schematic overview of the study procedures is outlined in figure 1. Note that this figure does not hold into account that it is possible for patients randomized to the treatment group to receive additional injections if necessary.

[figure not shown]

Fig.1 Flow diagram of study procedures

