4.2 Inclusion criteria

In order to be eligible to participate in this study, a subject must meet all of the following criteria:

- Sciatica;
- Leg pain of 6 or more on a 10 point NRS (Numeric Rating Scale) scale with a duration of >3 and <8 weeks;
- Patient is willing to accept the possible costs for the treatment by the pain physician
- Informed consent.

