6. METHODS

6.1 Study parameters/endpoints

6.1.1 Main study parameter/endpoint

NRS leg pain: The pain intensity in the leg and the back will be measured with a 10-point horizontal Numeric Rating Scale (NRS), ranging from 0 (no pain) to 10 (worst imaginable pain). During each visit the NRS leg pain and NRS back pain will be scored. The patient is not entitled to see the pain scores indicated during previous visit(s). The NRS scores will be measured at baseline and at 1, 2, 4, 10 and 21 weeks after randomization.

The average score for NRS leg pain at two weeks after injection is compared to the average score for NRS leg pain in the prolonged conservative care group, 2 weeks after randomization. This will be calculated again at 4 weeks after randomization.

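### The prediction analysis in section 8.2 leaves out baseline leg pain, so it cannot show that 2-week response adds to the pain score known before the injection

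*Combined protocol and SAP*

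**What the plan says.** Section 3 (Study design) documents as a successful effect of TEI "NRS leg pain that decreases below the value of 4 (on a 10 point scale) within two weeks after TEI". The cut-off is absolute and does not refer to the entry score. Section 4.2 admits patients with "Leg pain of 6 or more on a 10 point NRS (Numeric Rating Scale) scale".

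Section 2 gives the purpose. The hypothesis is that "being non-responsive to TEI within two weeks, predicts an unsatisfactory condition after 14-16 weeks of suffering", and the plan says that, if this is right, such patients could in future be offered surgery earlier. Section 2 also equates 10 and 21 weeks after randomisation with roughly 14-16 and 26 weeks after onset.

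Section 8.2 gives the analysis: "The 2-week success data will be correlated to the success data after 14 weeks and subsequently for 26 weeks using Chi-square tests to make predictions". It adds: "Logistic regression analysis will be used to correlate 2-week (and 4-week) success data to the absolute data for NRS leg pain", along with back pain, ODI and EQ-5D. No covariate is named for either analysis. Changes from baseline appear in 8.2 only as separate t-tests at 2 and 4 weeks. The correlations of early response with weeks 10 and 21 announced in section 2 have no baseline term either.

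Section 8.2 does not say that 2-week success means NRS below 4. The only success rule written there is for perceived recovery, where Likert 1 or 2 is a success. Baseline NRS leg pain is collected (section 6.1.1).

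**The concern.** Under the section 3 rule, response is partly a restatement of where the patient started. On whole-number scores, a patient entering at 6 succeeds with a fall to 3. A patient entering at 10 who falls to 4, a larger improvement, does not succeed. If milder entry pain also goes with lower scores at weeks 10 and 21, early and late success will be associated to some degree even if the reaction to the injection carries no information of its own.

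What is at stake is the use of TEI response as a predictor that might bring surgery forward. An injection is worth using for that purpose if the response tells the clinician more than the pain score available beforehand. A chi-square test cannot take a covariate and the logistic regression names none, so a significant result from either would leave that question open.

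**Working it through.** **The plan's own figure.** The documents give no number for the prediction analysis. Their only sample-size figure, for the primary t-test in section 4.4, reproduces: 2 × (1.960 + 1.282)² × 2.6² / 1.5² = 63.1, so 64 per group and 128 in total; 128 / 0.90 = 142.2, against the stated 142. The present point does not touch it.

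**Threshold arithmetic (NRS reading).** Below 4 means 3 or less on whole numbers. Fall needed: 6 − 3 = 3 points at entry 6; 10 − 3 = 7 points at entry 10.

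**How much association entry severity alone could produce.**

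Inputs from the plan: week-2 mean 4.0 and SD 2.6 in the TEI group (section 4.4); entry range 6 to 10; 64 patients.

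Assumptions, because the documents give no figures: entry mean 7.6 and SD 1.17; week-10 mean 3.5 and SD 2.6; analysis within the TEI group; weeks 2 and 10 linked only through entry pain, with slope b, the number of points carried over to each later score per extra entry point.

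Model for a patient with entry score x: week-2 score = 4.0 + b(x − 7.6) + error, with error SD s = √(2.6² − b² × 1.17²). Rounded scores below 4 are values under 3.5, so P(success | x) = Φ[(3.5 − 4.0 − b(x − 7.6)) / s]. The correlation with entry score is b × 1.17 / 2.6.

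Example, b = 1.0: s = √(6.76 − 1.37) = 2.32. Entry 6: Φ(1.1 / 2.32) = 68%. Entry 10: Φ(−2.9 / 2.32) = 11%.

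Example, b = 0.5: s = √(6.76 − 0.34) = 2.53. Entry 6: Φ(0.3 / 2.53) = 55%. Entry 10: Φ(−1.7 / 2.53) = 25%.

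Applying the same model to week 10 and cross-tabulating the two successes by simulation gives:

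| Slope b | Correlation with entry score | Odds ratio, early with late success | Unadjusted chi-square rejects (n = 64) |
|---|---|---|---|
| 0.25 | 0.11 | 1.03 | 5-6% |
| 0.5 | 0.23 | 1.14 | 6% |
| 0.75 | 0.34 | 1.36 | 9% |
| 1.0 | 0.45 | 1.73 | 18% |

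With b = 0 the odds ratio is 1.0 and rejection about 5%.

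**Sensitivity to the entry distribution.** With entry scores spread evenly over 6 to 10 (SD 1.41) and a week-10 mean of 3.0 or 4.0, the odds ratio is 1.22 with 6-7% rejection at b = 0.5, and 2.4 with 39-40% rejection at b = 1.0. With scores concentrated at 6 to 8 (SD 1.14) the corresponding figures are 1.13 with 6%, and 1.64-1.68 with 16-17%.

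**With the adjustment.** In these scenarios the odds ratio given entry score is 1.0 by construction. Simulated logistic regression with baseline NRS rejected in 4-6% of trials.

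**The case against.** Three counter-arguments have force.

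First, the success rule. Section 8.2 writes only the Likert rule, in the sentence just before the prediction test. Perceived recovery is not an NRS cut-off, so the 3-point against 7-point contrast and the simulation apply only if success means NRS below 4. This stands. What survives under either reading is that no baseline term is planned.

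Second, size. A reader might infer that entry severity by itself is likely to make the planned test significant, so that a positive finding would be an artefact. The documents do not support that. They give no entry distribution, no correlation with baseline and no week-10 mean or SD, and at partial carry-over the excess over 5% is slight. Assuming a correlation of 0.5 with an entry SD of 1.1 gives rejection near 25%, but it implies a slope of 0.5 × 2.6 / 1.1 = 1.18: each entry point would add more than a full point at both later times.

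Third, a raw predictor can be valid and useful while partly reflecting baseline. Section 2 hypothesises prediction and does not claim an increment over entry pain. The chi-square is therefore a legitimate description of raw prediction; it does not answer whether response adds anything.

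A reader might also infer that a baseline-adjusted association would show a TEI-specific signal. It would not. Section 3 notes that many patients recover without intervention, and an early spontaneous recoverer still counts as a responder after adjustment.

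**Conclusion.** The point holds in a limited form. As planned, the prediction analysis cannot show that 2-week response adds to entry pain, and this is true whichever success definition is meant and whatever the size of the baseline correlation. Under the NRS definition, entry severity can also contribute to the association itself. On the main assumptions (entry mean about 7.6 and SD about 1.2, week-10 mean 3.5 and SD 2.6, no link other than baseline) that contribution is an odds ratio of about 1.0 to 1.7, with rejection in about 5% to 18% of trials of 64 patients for slopes of 0.25 to 1.0. It becomes appreciable only if most of each entry point carries over; larger values need a wider spread of entry scores as well. It concerns a secondary analysis and does not make the planned test of raw association invalid.

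**What to change.** In section 8.2:

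- Name one definition of success, NRS below 4 or Likert 1-2, and use it at 2 weeks and at the later time points.
- Analyse success at weeks 10 and 21 by logistic regression on 2-week success, with baseline NRS leg pain as covariate. Report the adjusted odds ratio and the gain in c-statistic over baseline NRS alone.
- Keep the unadjusted chi-square as the description of raw prediction. Claim added predictive value over entry pain only from the adjusted model.
- State that the adjusted result is not specific to TEI, because baseline adjustment does not remove spontaneous recovery.

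State also when the baseline score is taken. Section 6.3 mentions randomisation before the hospital visit at which baseline data are gathered, while section 10.1 places baseline collection during inclusion, so a score recorded before allocation is not assured by the current wording.

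The cost is one degree of freedom, a few sentences of wording and possibly a smaller reported association. Baseline NRS is already among the planned measurements, and the sample size and primary analysis do not change.
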